8.1.13 Supplementary procedures for subjects

During the clinical trial, if the number of subjects fails to meet the statistical requirements due to dropout for any reason, or the investigator considers it necessary to supplement subjects, the reasons shall be analyzed firstly, and then the investigator, sponsor and statistician shall discuss whether to supplement or not. After determining the number of supplemented cases, the information shall be submitted to relevant departments for review.

8.1.14 Study completion criteria

Study completion refers to that the clinical study has included sufficient subjects according to the requirements of clinical protocol and completed the treatment, observation and evaluation for all subjects, and the collected data can be used to evaluate the safety and effectiveness of the study product.

8.1.15 Effectiveness evaluation method

8.1.15.1 Main effectiveness evaluation indicators, method and time for evaluation, recording and analysis

(1) Success rate of anastomosis

Justification for selection: According to the *Guidelines for Technical Review of Endoscopic Stapler Registration* issued by NMPA (original CFDA) on March 13, 2017, the "success rate of anastomosis" is selected as the primary evaluation indicator for such products.

Evaluation time: During the surgery.

Evaluation site: Tissues receiving linear stapler for gastrointestinal anastomosis.

Evaluation method: The transection and anastomosis of lung tissues are performed during the operation. The device is withdrawn after successful triggering. The cutting staple line is carefully checked for integrity, air leakage and bleeding. Anastomosis is considered as successful if all anastomotic rings are intact without leakage or bleeding, otherwise it is considered as failure. If necessary, the gas injection method is used to inspect whether there is bubble overflow at anastomotic stoma. If there is no bubble overflow, it is recorded as successful anastomosis; if there is obvious bubble overflow, it is recorded as anastomosis failure.

Formula: Anastomosis success rate = number of subjects with successful anastomosis in each group/total number of subjects in this group \times 100%

Precautions: During gastrointestinal tissue cutting and anastomosis, the subject may be converted into thoracotomy due to his complicated condition. At this time, the investigators need to determine whether the subject's conversion to thoracotomy is caused by the stapler. If it is caused by the stapler, it is judged as anastomosis failure. After gastrointestinal tissue anastomosis, the investigator may need to supplement the stitching treatment for anastomotic tissues. If the supplement is resulted from incomplete anastomosis ring, leakage and bleeding, it is considered as anastomosis failure.

8.1.15.2 Secondary effectiveness evaluation indicators, method and time for evaluation, recording and analysis

(1) Stapler-resulted conversion rate

Justification for selection: The need for conversion to thoracotomy due to failed anastomosis increases the risk to the subject. Therefore, the "stapler-resulted conversion rate" is selected as one of the effectiveness indicators of the product. At the same time, with reference to the *Guidelines for Technical Review of Endoscopic Stapler Registration* issued by NMPA (original CFDA) on March 13, 2017, the "stapler-resulted conversion rate" is selected as an effectiveness evaluation indicator for such products.

Evaluation time: During the surgery.

Evaluation method: Indicators of conversion to laparotomy are ① bleeding difficult to control; ② invasion of adjacent organs or blood vessels resulting in difficulty in surgery; ③ patients difficulty in tolerating pneumoperitoneum during surgery; ④ accidental injury of other organs during surgery, which are difficult for treatment; ⑤ severe intraoperative adhesions found during surgery. If the conversion to laparotomy is caused by the stapler, it should be recorded truthfully.

Formula: Stapler-resulted conversion rate = number of eligible subjects in each group/total number of subjects in this group \times 100%

(2) Number of stitches repaired with staple line

Justification for selection: When the stapler is used for gastrointestinal tissue anastomosis, the situation that

the staple line needs to be repaired may occur. When the number of repair needles becomes larger, it may increase the risk to the subject. Therefore, the "number of stitches repaired with staple line" is selected as one of the indicators to evaluate the effectiveness of the product. At the same time, with reference to the *Guidelines for Technical Review of Endoscopic Stapler Registration* issued by NMPA (original CFDA) on March 13, 2017, the "number of stitches repaired with staple line" is selected as an effectiveness evaluation indicator for such products.

Evaluation time: During the surgery.

Evaluation method: The number of staple line repair needles of each subject during operation is recorded.

Precautions: Anastomotic repair is required when the anastomotic ring is incomplete, leaking and bleeding. Anastomotic repair may also be necessary when there is a dehiscence of the staple line during surgery. Sometimes the investigators may perform anastomotic repair in order to strengthen the anastomotic site. Therefore, the reasons for repair should be recorded.

(3) Operation time

Justification for selection: The main purpose of stapler is to reduce the surgeon's operation intensity and save operation time. Therefore, the operation time is selected as one of the indicators to evaluate the product performance. Meanwhile, with reference to the *Guidelines for Technical Review of Endoscopic Stapler Registration* issued by NMPA (original CFDA) on March 13, 2017, the "operation time" is selected as the secondary evaluation indicator for such products.

Evaluation time: During the surgery.

Evaluation method: The investigators record the time taken from thoracotomy to chest closure to the nearest minute.

(4) Anastomosis time

Justification for selection: The main purpose of stapler is to reduce the surgeon's operation intensity and save operation time. Therefore, the stapling time is selected as one of the indicators to evaluate the product performance. Meanwhile, with reference to the *Guidelines for Technical Review of Endoscopic Stapler Registration* issued by NMPA (original CFDA) on March 13, 2017, the "anastomosis time" is selected as the secondary evaluation indicator for such products.

Evaluation time: During the surgery.

Evaluation method: The investigators record the time taken for the subject to perform the transection from the completion of mobilization of gastrointestinal tissues (the first operation site) to the completion of anastomosis of gastrointestinal tissues. The time is accurate to minutes.

(5) Anastomotic healing time

Justification for selection: Anastomotic healing is an important indicator for effectiveness and safety

evaluation of such products. Therefore, the anastomosis time is selected as one of the indicators to evaluate the product performance. Meanwhile, with reference to the *Guidelines for Technical Review of Endoscopic Stapler Registration* issued by NMPA (original CFDA) on March 13, 2017, eventually, the "anastomotic healing time" is used as a secondary indicator for evaluation.

Evaluation time: After surgery.

Evaluation method: The recovery of borborygmus and smooth eating and defectaion are considered as anastomotic healing. Only when the subjects meet these three criteria, it can be judged as the anastomotic healing, and the latest time observed shall be the basis for evaluation. The time is accurate to day.

(6) Time of first flatus

Justification for selection: After gastrointestinal surgery, anus exhaust indicates the gradual recovery of intestinal function and the gradual healing of anastomotic stoma, which is one of the markers for the gradual recovery of patients undergoing gastrointestinal surgery. Meanwhile, with reference to the *Guidelines for Technical Review of Endoscopic Stapler Registration* issued by NMPA (original CFDA) on March 13, 2017, the "time of first flatus" is selected as a secondary evaluation indicator for such products.

Evaluation time: After successful operation to before discharge.

Evaluation method: After the surgery, the investigators instructed the subjects to pay attention to the time of first anus exhaust. The subjects fed back to the physician after feeling the first flatus. The time is accurate to day.

(7) Time of first bowel movement

Justification for selection: After gastrointestinal surgery, the intestinal function gradually recovers. When the patients can recover spontaneous defecation, it indicates that the anastomotic stoma gradually heals, which is one of the markers for the gradual recovery of patients undergoing gastrointestinal surgery. Meanwhile, with reference to the *Guidelines for Technical Review of Endoscopic Stapler Registration* issued by NMPA (original CFDA) on March 13, 2017, the "time of first bowel movement" is selected as a secondary evaluation indicator for such products.

Evaluation time: After successful operation to before discharge.

Evaluation method: The investigators observed the time for subjects to recover spontaneous defectaion for the first time after operation. The time is accurate to day.

(8) Time of eating semi-liquid food

Justification for selection: After gastrointestinal surgery, the intestinal function gradually recovers when the patients eat semi-liquid food, which indicates that anastomotic stoma gradually heals, which is one of the markers for patients undergoing gastrointestinal surgery. Meanwhile, with reference to the *Guidelines for Technical Review of Endoscopic Stapler Registration* issued by NMPA (original CFDA) on March 13, 2017,

the "time of eating semi-liquid food" is selected as a secondary evaluation indicator for such products.

Evaluation time: After successful operation to before discharge.

Evaluation method: The investigators determine whether the subject can eat semi-liquid food according to his/her recovery, and record the time of eating semi-liquid food. The time is accurate to day.

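### The primary-endpoint scoring rule (8.1.15.1) names only thoracotomy as a failing conversion in a trial that records laparotomy, and its gas-test sentence conflicts with its general failure rule

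*Combined protocol and SAP*

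**What the plan says.** Section 8.1.15.1 is evaluated during surgery and contains these rules:

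- **Check and general rule.** "The cutting staple line is carefully checked for integrity, air leakage and bleeding" and then "Anastomosis is considered as successful if all anastomotic rings are intact without leakage or bleeding, otherwise it is considered as failure".
- **Gas test, used only if necessary.** "If there is no bubble overflow, it is recorded as successful anastomosis; if there is obvious bubble overflow, it is recorded as anastomosis failure".
- **Conversion.** "At this time, the investigators need to determine whether the subject's conversion to thoracotomy is caused by the stapler"; if it is, the anastomosis counts as failed.
- **Repair.** Extra stitching for an incomplete ring, leakage or bleeding counts as failure.
- **Site and tissue.** The evaluation-site line names gastrointestinal anastomosis, but the method sentence reads "The transection and anastomosis of lung tissues are performed during the operation".

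In 8.1.15.2, the secondary indicator for stapler-related conversion is justified with "The need for conversion to thoracotomy due to failed anastomosis increases the risk to the subject". Its evaluation method then lists indicators of conversion to laparotomy and ends with "If the conversion to laparotomy is caused by the stapler, it should be recorded truthfully". Operation time, in the same section, is defined thus: "The investigators record the time taken from thoracotomy to chest closure to the nearest minute".

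Section 8.2.5.5 collects indicators of conversion to laparotomy. It also collects ring completeness, leakage, bleeding and bubble overflow as separate items, and the start and end of the operation. Footnote 11 asks for the reason for a conversion and its relation to the stapler. Footnote 13 asks whether each reload was used laparoscopically or in open surgery. Section 8.2.4 states that investigators cannot be blinded.

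**The concern.** Wording from a thoracic protocol appears to have been carried into the rule that decides the trial. Two consequences affect scoring.

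First, the conversion the trial is set up to record is not the one the primary endpoint fails. The text on laparotomy asks for it to be recorded but does not link it to primary failure.

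Second, the gas-test sentence and the general rule can give opposite scores for the same subject.

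A smaller third point is that the gas-test sentence fails only obvious bubbling, although the general rule fails any leakage.

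Five institutions must apply one rule during surgery, with the arm known and few failures expected. Where the text gives no answer or two answers, the score depends on the person scoring.

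**Working it through.** **1. Cases set against the rules**

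| Finding | Rule giving success | Rule giving failure | Score as written |
|---|---|---|---|
| Stapler-caused thoracotomy, sound line | general rule | conversion rule | failure |
| Stapler-caused laparotomy, sound line, no repair for a defect | general rule | none | success if read literally |
| Stapler-caused laparotomy, line incomplete, leaking or bleeding, or repaired for that | none | general or repair rule | failure |
| Line bleeding or incomplete, gas test negative | gas-test sentence | general rule | both |
| Slight, not obvious, bubbling | none | general rule, if counted as leakage | gas-test sentence silent |
| No gas test done | general rule | general rule | one answer |

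The defects are rows 2 and 4, with row 5 minor.

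**2. The plan's own sample size**

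Inputs from 9.2.1: 97% in both arms, margin 10%, one-sided 0.025, power 80%.

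- n = 2 × 0.97 × 0.03 × (1.960 + 0.842)² / 0.10² = 45.7, so 46.
- Correction: 46/4 × (1 + √(1 + 4/(0.10 × 46)))² = 64.4, so 65.
- Dropout: 65/0.80 = 81.25, so 82 per arm and 164 in total.

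All three figures reproduce. This point disputes no number in the plan.

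**3. How few subjects decide the result (illustration)**

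Expected failures per arm are 82 × 0.03 = 2.46, or 65 × 0.03 = 1.95. Section 9.5 requires the lower 95% limit of the difference to exceed −10%. The plan does not name the interval method, so two are shown, each with 2 control failures.

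| Per arm | Test failures | Wald | Newcombe |
|---|---|---|---|
| 82 | 4 | −8.2% | −9.7% |
| 82 | 5 | −9.8% | −11.3% |
| 82 | 6 | −11.4% | −12.8% |
| 65 | 3 | −8.1% | −9.9% |
| 65 | 4 | −10.3% | −12.0% |

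Wald example, 5 against 2 of 82: 77/82 − 80/82 = −0.0366. The standard error is √(0.000698 + 0.000290) = 0.0314, and −0.0366 − 1.96 × 0.0314 = −0.098.

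Near the boundary, one subject scored differently reverses the conclusion.

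**4. Effect of one score at the margin (assumed scenario)**

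Assume true success of 87% against 97%, 82 per arm, and exact binomial enumeration. The chance of wrongly declaring non-inferiority is:

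| Rescoring | Newcombe | Wald |
|---|---|---|
| none | 2.1% | 4.3% |
| one test-arm failure called success | 4.7% | 8.7% |
| one failure called success in each arm, where both have one | 2.8% | 6.2% |

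**The case against.** The strongest reply is that the intent is clear and the general rule does most of the work.

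- **Conversion.** Section 8.1.15.2 uses thoracotomy and laparotomy for one indicator, which suggests that the primary rule means any open conversion. The line is checked once the device is withdrawn, so one that was defective then and later repaired still fails. This narrows the gap to row 2 of the first table, but the failure rule still does not state the intent.
- **Gas test.** It is an optional addition to a rule that already ends with failure for anything short of intact, dry and leak-free. The repair sentence after it says again that bleeding and leakage are failures, and 8.2.5.5 records each finding separately. A coherent reading therefore exists, but it is left to the reader.
- **Traceability.** Reasons for conversion and repair are recorded, so affected subjects can be found before database lock. That is a real safeguard, but it does not say how to score them.
- **Fragility.** The figures would hold for any trial near its margin, and the largest rise assumes that rescoring happens in the test arm only. This objection stands in full: the figures say nothing about how often these cases occur.

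A reader might go further and infer that the endpoint is assessed on the wrong organ. The documents do not support that, because the evaluation-site line names gastrointestinal anastomosis and no subject is scored differently because of the lung wording. A reader might also infer that a negative gas test is meant to override bleeding. The text shows an unresolved conflict, not that intention.

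**Conclusion.** The scoring rule is inconsistent as written and should be fixed. Two identifiable situations lack a single correct score: a stapler-caused laparotomy with no line defect, and a defective line with a negative gas test. The treatment of slight bubbling is a minor addition. The lung wording has no scoring consequence, and the operation-time definition affects only a secondary indicator.

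The conclusion rests on the text. The number of subjects affected cannot be derived from the documents, and most gross failures are already caught. It would be too strong to say that the endpoint is invalid or that the false-positive rate is inflated by a known amount: the rise from 2.1% to 4.7% (Newcombe) or from 4.3% to 8.7% (Wald) depends on an assumed true difference at the margin and one assumed one-sided rescoring. Unblinded scoring makes such asymmetry possible, but nothing shows that it occurs.

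**What to change.** Reconcile 8.1.15.1 and 8.1.15.2 with 8.2.5.5 and its footnotes into one scoring rule that:

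1. counts any stapler-caused conversion to open surgery as failure, adding laparotomy alongside thoracotomy. Substituting laparotomy alone could drop a listed failure, since 9.2.1 refers to anastomosis from the esophageal site;
2. states that a negative gas test does not override an incomplete line, leakage or bleeding;
3. states how non-obvious bubbling is scored, consistently with the leakage rule;
4. replaces the lung wording with gastrointestinal tissue.

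Separately, define operation time by the start and end times already collected.

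The cost is protocol and CRF wording, with no new procedure, visit or staff. The downside is that slightly more events may count as failures. One more per arm of 82 means a failure rate of 0.03 + 1/82 = 0.042, or about 95.8% success. Power at equal rates would then fall from about 86% to 79% (Newcombe) or from 95% to 89% (Wald).

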Sample Size	cases in both the test group and control group, respectively
Center Number	5
Follow-up period:	37 days
	(1) Enrollment date of the first subject: June 2018
Test Time	(2) Duration of subject recruitment: 6 months
	(3) Completion date of the last subject: December 2018
Primary Effectiveness	(1) Success rate of anastomosis

Evaluation Indicator	
	(1) Conversion rate due to stapler-related causes
	(2) Number of stitches for anastomotic repair
Secondary	(3) Operation time
Effectiveness	(4) Anastomosis time
Evaluation Indicator	(5) Anastomotic healing time
Evaluation indicator	(6) First flatus time
	(7) First bowel movement time
	(8) Semi-liquid diet time
	(1) Incidence of anastomotic dehiscence
	(2) Incidence of anastomotic bleeding
Safety Evaluation	(3) Incidence of anastomotic leakage
Indicator	(4) Incidence of anastomotic stricture
indicator	(5) Incidence of anastomotic infection
	(6) Incidence of SAEs
	(7) Incidence of AEs
Operational	
Performance	(1) Stapler operational performance evaluation
Evaluation	
	(1) Subjects aged 18-75 years old, male or female;
	(2) Subjects who are intended to undergo gastrointestinal tissue cutting and
Inclusion Criteria	anastomosis with linear stapler;
inclusion Criteria	(3) Subjects or their guardians are able to understand the purpose of the study,
	show adequate compliance with the trial protocol, and sign an informed
	consent.
	(1) Subjects who are scheduled to receive gastrointestinal emergency surgery;
	(2) Subjects with moderate malnutrition (BMI < 17 kg/m²) and severe anemia
	(Hb < 60 g/L);
Exclusion Criteria	(3) Subjects with a BMI $\geq 28 \text{ kg/m}^2$;
Exclusion Criteria	(4) Subjects who have a platelet (PLT) $< 60 \times 10^{9}$ /L or international normalized
	ratio (INR) > 1.5;
	(5) Subjects with forced expiratory volume in one second (FEV1)/predicted
	value $\leq 50\%$, or forced expiratory volume in one second (FEV1)/forced vital

capacity (FCV) $\leq 60\%$;

- (6) Subjects with ejection fraction $\leq 50\%$;
- (7) Subjects with important organ failure or other serious diseases (e.g., the subject's aspartate aminotransferase (AST), alanine aminotransferase (ALT), or serum creatinine (Scr) is more than 3 times of the upper limit of normal before surgery; the subject's fasting blood glucose value before surgery is ≥ 10.0 mmol/L);
- (8) Subjects who are pregnant or lactating women;
- (9) Subject who have participated in other drug or device clinical trials within 3 months prior to the trial;

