8.1.6.2 Inclusion criteria

Subjects meeting all of the following conditions only can be included:

- (1) Subjects are aged 18-70 years (inclusive), male or female;
- (2) Subjects are scheduled to accept gastrointestinal tissue cutting and anastomosis;
- (3) Subjects or their guardians are able to understand the purpose of the study, show adequate compliance with the trial protocol, and sign an ICF.

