8.1.6.3 Exclusion criteria

Subjects meeting any of the following conditions can not be included:

- (1) Subjects who are scheduled to receive gastrointestinal emergency surgery;
- (2) Subjects with moderate malnutrition (BMI \leq 17 kg/m²) and severe anemia (Hb \leq 60 g/L);
- (3) Subjects with a BMI \geq 28 kg/m²;
- (4) Subjects with platelet (PLT) $< 60 \times 10^{9}$ /L or international normalized ratio (INR) > 1.5;
- (5) Subjects with a forced expiratory volume in one second (FEV1)/predicted value ≤ 50%, or a forced expiratory volume in one second (FEV1)/forced vital capacity (FCV) ≤ 60%;
- (6) Subjects with ejection fraction $\leq 50\%$;
- (7) Subjects with important organ failure or other serious diseases (e.g., the subject's aspartate aminotransferase (AST), alanine aminotransferase (ALT), or serum creatinine (Scr) is more than 3 times of the upper limit of normal before surgery; the subject's fasting blood glucose value before surgery is ≥ 10.0 mmol/L);
- (8) Subjects who are pregnant or lactating women;
- (9) Subjects who have participated in other drug or device clinical trials within 3 months prior to the trial;
- (10)Other situations not suitable for inclusion judged by the investigators.

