8.2.5 Inspection items

8.2.5.1 Medical history and vital signs

- (1) Demographic data: gender, date of birth;
- (2) History of present illness: admission time, surgical site ³;
- (3) Past medical history: allergy history, dysfunction history of vital organs (heart, lung, liver and kidney), surgery history, and previous medication history ⁴ (within 1 month);
- (4) Vital signs: height, weight, blood pressure, pulse, temperature, respiration, BMI ⁵;

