8.2.6 Device using specification

According to the results of random allocation, the investigators apply the study medical device to the subjects who enter the test group, and the control medical device to the subjects who enter the control group. If a subject requires the use of a circular stapler during the trial, the brand and model of the circular stapler shall be recorded.

⁹ Only the conditions related to the use of test product and control product are recorded here. However, during the trial, subjects may use circular stapler or other staplers. If adverse events related to the stapler also occur, the occurrence shall be truthfully recorded in the adverse events.

¹⁰ It is necessary to use gas injection method for inspection. If relevant examination is not required, the CRF should be completed as "Not Applicable".

¹¹ If yes, please specify the reason and whether it is related to the stapler.

¹² The model and amount used in the clinical trial shall be truthfully recorded. Meanwhile, whether the subject uses the brand and model of circular stapler shall also be collected.

¹³ Investigators faithfully record whether each reload is used laparoscopically or laparotomically.

¹⁴ The tissues cut and anastomosed by each cartridge, such as stomach, duodenum, jejunum, ileum, appendix, ascending colon, transverse colon, descending colon, sigmoid colon and rectum, etc. are recorded.

¹⁵ If corresponding symptoms occur, the reasons for confirming the event should also be briefly described, so as to facilitate the review. In addition, generally anastomotic bleeding is judged by the presence or absence of persistent fresh bleeding from the gastric tube, and the diagnosis is confirmed by gastroscopy or second surgical exploration.

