9.2 Sample Size Calculation

9.2.1 Total sample size

164 subjects are planned to be enrolled in this clinical trial. The sample size determination process is as follows:

This clinical study is a parallel positive control clinical validation design. The "anastomosis success rate" is adopted as the basis for sample size estimation. Based on literature review [3-11], the success rate of anastomosis is up to 100% when the similar devices are used for total laparoscopic distal gastrectomy for gastric cancer. According to relevant literatures and considering clinical practice, when such products are used for anastomosis from esophageal site to gastrointestinal site, the "success rate of anastomosis" can reach 97%. Therefore, the "anastomosis success rate" of this clinical trial is determined to be 97% with a clinical non-inferiority margin of 10%. The parameters are set as follows: $\alpha = 0.025$ (one-sided), $\beta = 0.2$, $\delta = 10\%$, and the ratio of test control group is 1:1. The estimation formula of sample size for non-inferiority clinical validation is adopted, and the sample size required in each group is at least 65 cases. The calculation formula [12] and correction formula [13] are as follows:

$$\begin{split} n_{A} &= \frac{(\pi_{A}(1-\pi_{A}) + \pi_{B}(1-\pi_{B}))(Z_{1-\beta} + Z_{1-\alpha})^{2}}{((\pi_{A} - \pi_{B}) - d)^{2}} \\ n_{B} &= \frac{n_{3} \left\{ 1 + \left[1 + 4/(\delta n_{A}) \right]^{\frac{1}{2}} \right\}^{2}}{4} \end{split}$$

Considering that the number of subjects who may drop out or be lost to follow-up during clinical validation is about 20%, the sample size of each group is expanded to 82 cases, and the total sample size required for the two groups is 164 cases.

9.2.2 Number of cases for clinical trial of each disease and reasons for determination

The investigational product is mainly used for the cutting and anastomosis of gastrointestinal tissues, other diseases therefore are not involved in this clinical trial.

9.2.3 Minimum and maximum number of subjects in each clinical trial institution and reason

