9.7.1 Statistical method for data

Statistical analysis is performed using the SAS 9.1 software.

Statistical description on all data, including demographic data, baseline data, all efficacy indicators and all safety data shall be performed. Measurement data will be statistically described using mean, standard deviation, minimum, maximum, median, 25th percentile and 75th percentile; enumeration data will be statistically described using frequency and percentage.

The primary effectiveness evaluation indicator (anastomosis success rate) is evaluated by the confidence interval method.

The secondary evaluation indicators are evaluated by the difference test. Measurement data are compared using two independent samples t-test or Wilcoxon rank sum test. Enumeration data are compared using Pearson's X^2 test or Fisher's exact test.

The safety evaluation indicators are evaluated by the difference test. Enumeration data are compared using Pearson's X^2 test or Fisher's exact test. The adverse events and device defects occur in this trial shall be shown in list.

The stapler operational performance is evaluated by the difference test. Enumeration data are compared using Pearson's X^2 test or Fisher's exact test.

The central effect is considered in the analysis process. The general linear model is used for measurement data, and CMH or logistic regression is used for enumeration data.

9.7.2 Missing, unused, or incorrect data (including dropouts and withdrawals) and unreasonable data

All missing, unused or incorrect data (including dropouts and withdrawals) and unreasonable data will be discussed and finally determined by the investigators and biostatistician in the data review stage. The basic statistical principles for the processing of these data are as follows:

- (1) The details of each drop-out case shall be described, and the drop-out between the test group and the control group shall be compared using Pearson X^2 test or Fisher exact test;
- (2) Missing data at baseline shall not be estimated;
- (3) Missing values of main evaluation indicator (success rate of anastomosis) shall not be estimated;

Clinical Trial on Performance and Safety of Disposable Powered Articulating Endoscopic Linear Cutter Stapler in Gastrointestinal Tissue Cutting and Anastomosis

- (4) Missing values of secondary evaluation indicators shall not be estimated;
- (5) Missing values for operational performance evaluation shall not estimated;

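### Surgical site and planned approach enter neither the time-endpoint analyses nor the conversion-rate denominator, which costs precision and may dilute one reported rate

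*Combined protocol and SAP*

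**What the plan says.** **Who enters.** Inclusion criterion (2) in Section 8.1.6.2 reads "Subjects are scheduled to accept gastrointestinal tissue cutting and anastomosis". The abstract's version adds only that a linear stapler will be used. The one exclusion in Section 8.1.6.3 that concerns the surgical setting is "Subjects who are scheduled to receive gastrointestinal emergency surgery". No organ, operation or approach is specified.

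**What is expected in theatre.** Footnote 13 (to Section 8.2.5.5 (3)) says "Investigators faithfully record whether each reload is used laparoscopically or laparotomically". Footnote 14 lists tissues from stomach through appendix and colon to rectum. Section 8.1.5.1 foresees rectal cases that also need a circular stapler. The planning text is narrower: Section 9.2.1 relies on reports that "the success rate of anastomosis is up to 100% when the similar devices are used for total laparoscopic distal gastrectomy for gastric cancer", and Section 8.1.4 (3) discusses experience with total laparoscopic reconstruction.

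**Conversion endpoint.** Section 8.1.15.2 (1) gives "Stapler-resulted conversion rate = number of eligible subjects in each group/total number of subjects in this group". Its listed indicators are for conversion to laparotomy, and one of them is intolerance of pneumoperitoneum.

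**Time endpoints.** Section 9.7.1 names a two-sample t-test or a Wilcoxon rank sum test for measurement data. It then says that the centre effect is considered: "The general linear model is used for measurement data". Randomisation is stratified by centre alone (Sections 8.1.3 (3) and 8.2.3).

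**Data collected.** Section 8.2.5.1 lists "History of present illness: admission time, surgical site", and footnote 3 lets that item be completed after surgery. The name of the operation is recorded during surgery (Section 8.2.5.5 (1)). Approach is recorded per reload, not as a plan per subject.

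**Reading of results.** Under Section 9.5, p > 0.05 on a secondary indicator means no significant difference between the groups.

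**The concern.** Operation time, anastomosis time and the recovery times can be expected to differ between, say, a gastric and a rectal operation, and between open and laparoscopic surgery. If neither factor is in the analysis, that variation sits in the error term. A real difference between devices is then harder to see, and a chance imbalance in case mix is not corrected. Because a non-significant result is reported as no difference, lost precision leans towards a finding of similarity. Section 8.1.15.2 (3) and (4) justify the operation and anastomosis times by the stapler's purpose of saving operating time, so these endpoints bear on what is claimed for the device.

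The conversion rate raises a separate question of definition. A subject whose operation is planned as open is not at risk of conversion but is counted in the denominator. The reported rate then depends on the open share as well as on the device.

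**Working it through.** **1. The plan's own figure.** The documents give no figure for the conversion or time endpoints; the only one to reproduce is the primary sample size. With 97% success in both arms, a 10% margin, one-sided alpha 0.025 and 80% power, the basic formula gives 45.68, so 46. The correction n/4 × (1 + √(1 + 4/(δn)))² with n = 46 and δ = 0.10 gives 64.4, so 65. Then 65/0.8 = 81.25, so 82 per group and 164 in total. This matches Section 9.2.1 and does not depend on the present point.

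**2. Time endpoints.** Let R² be the share of the variance left after centre that surgical site and approach explain. Adjustment multiplies the standard error of the arm difference by √(1 − R²). For power, take 82 per arm and a true difference of 0.44 within-procedure standard deviations. The adjusted analysis has 0.44/√(2/82) = 2.817, and 2.817 − 1.96 = 0.857, so about 80% power. Leaving the factors out gives Φ(2.817 × √(1 − R²) − 1.96).

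| Assumed R² | Cut in standard error from adjusting | Power without adjusting |
|---|---|---|
| 0.2 | 11% | 71% |
| 0.3 | 16% | 65% |
| 0.4 | 23% | 59% |
| 0.5 | 29% | 51% |

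These cuts assume that R² is counted beyond centre. If hospitals differ in case mix, centre already absorbs part of it. For illustration, suppose centre alone explains 20% and all terms together explain 30-50%. Then the ratio is √(0.7/0.8) = 0.94 to √(0.5/0.8) = 0.79, a cut of 6-21%.

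**3. Chance imbalance.** Treat allocation as simple randomisation and assume that 25% of subjects are planned open. The 95% range for the between-arm difference in open share is ±1.96 × √(2 × 0.25 × 0.75/82) = ±13 percentage points. The mean is zero, so this is a source of variance and not of bias.

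**4. Conversion rate.** With laparoscopic share f, the reported rate is f times the rate among those at risk, and so is the absolute difference. Assume a true rate of 3%. With 10% open, 3% × 0.9 = 2.7%; with 40% open, 3% × 0.6 = 1.8%.

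The test is another matter, because the event counts are the same under either denominator. For five conversions against none, Fisher's exact test gives p = 0.059 over 82 per arm and p = 0.056 over 49 per arm (f = 0.6). For assumed at-risk rates of 10% and 1%, power is as follows.

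| f | Subjects at risk per arm | Power, all subjects | Power, at-risk subjects only |
|---|---|---|---|
| 0.8 | 66 | 0.465 | 0.470 |
| 0.6 | 49 | 0.263 | 0.259 |
| 0.4 | 33 | 0.084 | 0.080 |

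So the denominator alters the reported rate and hardly alters the comparison.

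**The case against.** Several points on the other side stand.

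- **Size.** A reader might infer that procedure mix swamps the time endpoints. No standard deviation, variance share or case mix appears in the documents, so only the direction is established.
- **Bias.** A reader might infer that the time comparisons are biased. Randomisation balances site and approach in expectation, and the unadjusted test keeps its nominal 5% error rate. Chance imbalance is part of that error rate.
- **Open enrolment.** A reader might take footnote 13 as proof that planned open cases will be enrolled. It records approach per reload, which also fits reloads fired after a conversion or in an assisted step. The wide scope statement in Section 8.1.6.1 describes the product, and the text then narrows the trial to gastrointestinal surgery. Open cases are permitted, but their share could be near zero.
- **Conversion endpoint.** An all-subject rate is a legitimate quantity. Section 8.1.15.1 already counts every stapler-caused conversion as an anastomosis failure, so no event is lost.
- **Deferred detail.** Section 9.1 leaves methods to an analysis plan finalised before database lock, and that plan could add terms. This does not remove the point. Section 9.8 makes analyses outside that plan exploratory, and a baseline planned approach cannot be added reliably once surgery is over, because a converted case will also show open use.
- **Reading of p > 0.05.** Section 9.5 does not literally claim equivalence. Even so, with weak precision such a result says little.

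**Conclusion.** The point holds as a modest, inexpensive improvement to the secondary endpoints.

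For the time endpoints, the stated methods leave out two predictors of likely importance, so the comparisons carry avoidable noise. If site and approach explain 30-50% of the variance beyond centre, the standard error is 16-29% smaller after adjustment, and the gain shrinks as centre absorbs more of the case mix. Both the variance share and the overlap with centre are assumptions.

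For the conversion rate, the reported rate and absolute difference shrink in proportion to the planned-open share. On an assumed 3% rate with an assumed 10-40% open, that is 0.3 to 1.2 percentage points. With no open cases, the effect vanishes. The between-arm test is essentially unchanged in every case examined.

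Nothing here touches the primary non-inferiority analysis or the 65, 82 and 164 of Section 9.2.1.

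**What to change.** 1. Record planned surgical site and planned approach (laparoscopic or open) for each subject at screening, before the randomisation envelope is opened. This replaces the allowance in footnote 3 that site be completed after surgery, when the investigator knows the allocation.
2. In the analysis plan, add both factors, with centre, to the general linear model for operation time and anastomosis time. The recovery times are recorded in whole days: use the same model or, where the Wilcoxon test would be used, a stratified rank test (van Elteren). State which analysis leads, since Section 9.7.1 names both an unadjusted test and a model without ranking them.
3. Report stapler-caused conversions over the subjects in each group whose operation was planned laparoscopically, with the all-subject rate alongside.

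The cost is one or two case report form fields and a few lines in the analysis plan. The at-risk conversion rate has a smaller denominator, and reporting both rates covers that. No extra subjects are needed.
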